## Revision History

Protocol Version	Date	Amendments
1.0	28.03.2019	N/A – Original Protocol
2.0	09.05.2019	Removed the inclusion criteria statement that the informed consent form may be signed by a “legal representative”.
3.0	09.12.2020	1. Timing of obtaining consent modified to allow consenting of participants after they undergo EVAR (within 30 days of procedure), if it was not possible to obtain consent pre-operatively. 2. The location of the Core Lab corrected from Liverpool University to Liverpool University Hospitals NHS Foundation Trust. 3. Study timeline revised and extended (due to pandemic delays)
3.1	11.11.2021	The maximum number of patients recruited per site revised from 20 patients to 30 patients. Competitive recruitment remains in place ( Non-substantial amendment, no study-wide review required )

### Clinical Queries

Clinical queries should be directed to either the Local Principal Investigator or the Study Coordinator who will direct the query to the appropriate person.

## **Funder**

The British Society of Endovascular Therapy (BSET) has received funds from W.L. Gore & Associates, Inc. to carry out this prospective, investigator-initiated study. BSET and the Sponsor (Imperial College London) will have full responsibility for the conduct of the study.

This protocol describes the BSET-CLEVAR study and provides information about procedures for entering participants. Every care was taken in its drafting, but corrections or amendments may be necessary. These will be circulated to investigators in the study. Problems relating to this study should be referred, in the first instance, to the Chief Investigator.

This study will adhere to the principles outlined in the UK Policy Frame Work for Health and Social Care Research. It will be conducted in compliance with the protocol, the Data Protection Act and other regulatory requirements as appropriate.

## Study Summary

**DESIGN** A prospective, multicenter, observational cohort study of patients treated with the GORE EXCLUDER Conformable AAA Endoprosthesis **with ACTIVE CONTROL System** (EXCC Device)

**AIMS** The primary objective is to collect real-world clinical data and device specific outcomes of EXCC device in routine clinical treatment of abdominal aortic aneurysm (AAA).

**OUTCOME MEASURES** **Primary endpoint**

Evaluation of positioning accuracy and aortic neck coverage expressed as percentage of the total aortic neck assessed by CT scan between 4 weeks and 3 months follow-up\*

**Secondary endpoints**

- Technical success, defined as successful access and deployment of all required EXCC Device components
- In-hospital mortality
- Adjuncts to deal with type 1 endoleak at primary procedure
- Freedom from Type 1 or 3 endoleak at end of procedure, by 3\* months and around 1\* year
- 1-year aneurysm-related re-intervention rates
- 1-year aneurysm-related mortality

**POPULATION** Up to 200 patients presenting with abdominal aortic aneurysm (AAA) to the study centres (up to 30 NHS hospitals affiliated to BSET in the United Kingdom)

**ELIGIBILITY** Patients with AAA who are suitable for endovascular repair of their AAA and are either being considered for or have received treatment by endoprosthesis implantation

**DURATION** Approximately 38 months, including 12-month follow-up

\* Timelines for the first and final follow-up are flexible: First follow-up, including CT scan imaging, may be carried out between 4 weeks and 3 months and second (final) follow-up, including either a CT scan or duplex U/S imaging (depending on local EVAR surveillance policy), may be done at 12 months ± 4 weeks.

## **1. INTRODUCTION**

### **1.1 BACKGROUND**

#### **Disease**

Abdominal aortic aneurysm (AAA) is a degenerative disease of the aorta. It has been estimated that the overall prevalence of AAA in the European population is 4-5%, and is associated with increasing age, male sex, a history of smoking, high blood pressure and hypercholesterolaemia. A family history of aneurysmal disease also contributes to the risk of AAA, as do the presence of peripheral vascular disease, chronic obstructive pulmonary disease and coronary artery disease.

Rupture of an AAA is responsible for approximately 1-2% of all male deaths over the age of 65 years. The AAA prevalence is approximately three times higher in men than in women, although the rupture rate is approximately three times higher in women than it is for men.

#### **Historical Treatments**

Endovascular aneurysm repair (EVAR) is a minimally invasive procedure designed to exclude an aneurysmal segment of the aorta from blood circulation, and is a well-established treatment for AAA. This minimally invasive approach to open surgical repair has led to a significant reduction in morbidity and mortality in the short term^4-6. However, the durability of EVAR remains a concern, with late failure leading to rupture, and it is hoped that device evolution may lead to improved outcomes. The EVAR procedure involves delivery of a stent graft compressed onto a catheter to an aneurysmal segment of the aorta from a remote access site, generally the femoral artery. EVAR was first described in 1991 by Juan Parodi. Since that time, EVAR for the treatment of AAA has shown a lower operative and aneurysm related mortality in numerous clinical trials when compared with open surgical repair. These results have led to the widespread adoption of the EVAR procedure in patients with infrarenal AAA.

All endovascular devices are designed and tested for use in defined range of anatomies, described in the respective Instructions For Use (IFU) for each device. However, these anatomical criteria describe a subset of all patients that present with AAA and so use in patients outside of the IFU is common in order to treat to broadest range of patients. To facilitate this, interventionists have developed a range of off-label endovascular techniques which can extend the potential pool of patients eligible for endovascular treatment. However, use of the devices outside of IFU indications and with adjunctive

techniques such as chimney grafts can compromise the durability of the repair and may be associated with a higher risk of complications. Patients treated with 'hostile' neck anatomy, often with more severe neck angulation or shorter effective proximal sealing zones are at increased risk for operative morbidity, additional adjunctive procedures at treatment, Type I endoleak at one year, and aneurysm related mortality at one year.

The continued off-label use of endovascular stent grafts to treat patient populations with challenging anatomy suggests a need for improved endovascular stent grafts so that these patients can be treated safely and effectively in line with the manufacturer's intentions, the graft design and testing, and the indications provided in the Instructions For Use.

## **1.2 RATIONALE FOR CURRENT STUDY**

### **Study Device Description**

The GORE EXCLUDER AAA Endoprosthesis is a stent graft device that has accrued 20 years of worldwide experience with more than 285,000 devices implanted. Extensive clinical and commercial data has proven it to be a safe, effective and durable treatment for AAA.

The GORE® EXCLUDER® Conformable AAA Endoprosthesis *with ACTIVE CONTROL System* (EXCC Device), which is CE Mark approved, is an evolution of this device with a modified trunk design that enhances its ability to conform to the specific patient aortic neck anatomy. This has the potential to allow more accurate deployment, greater neck coverage and sealing zone especially in more angulated anatomy and improved durability of treatment.

The EXCC Device provides endovascular treatment of infrarenal AAA. It is a self-expanding stent graft that is constrained onto a delivery catheter which is used to advance and deploy the stent graft at the target location. The EXCC Device is a multi-component system consisting of a Trunk-Ipsilateral Leg Endoprosthesis, a Contralateral Leg Endoprosthesis, an Aortic Extender Endoprosthesis for proximal extension, and an Iliac Extender Endoprosthesis for distal extension. The graft material consists of expanded polytetrafluoroethylene (ePTFE) and fluorinated ethylene propylene (FEP) that is supported by nitinol (nickel titanium alloy) wire along its external surface. Nitinol anchors and an ePTFE / FEP sealing cuff are located at the leading (proximal) end of the trunk and a sealing cuff is located at the leading (proximal) end of the Aortic Extender. All components have gold radiopaque markers for visualization. ePTFE / FEP sleeves are used to constrain the endoprostheses on the delivery catheter.

Controlled deployment of the device is enabled with a staged deployment system including optional angulation control.

## **2. STUDY OBJECTIVES**

### **Primary Objective(s)**

The primary objective is to collect device-specific performance outcomes of GORE EXCLUDER Conformable AAA Endoprosthesis with ACTIVE CONTROL System in routine clinical treatment of abdominal aortic aneurysm.

### **Secondary Objective(s)**

The secondary objective(s) are assessment of technical and clinical success, as well as the evaluation of real-world clinical outcomes of GORE EXCLUDER Conformable AAA Endoprosthesis with ACTIVE CONTROL System in routine clinical treatment of abdominal aortic aneurysm.

## **3. STUDY DESIGN**

### **3.1 DESCRIPTION OF STUDY DESIGN**

The study is a prospective multicenter observational cohort registry of patients treated with the GORE® EXCLUDER® Conformable AAA Endoprosthesis with ACTIVE CONTROL System in the UK. Recruitment will take place in up to 30 experienced UK centers with extensive EVAR experience and implanted five or more GORE endoprosthesis. Up to 200 patients will be recruited and followed up for 1-year. It is anticipated recruitment will be complete in ~2 years and that the study will run for ~ 3 years. The maximum number of subjects enrolled per site is 30. All screened patients will have been previously evaluated in a standard manner (as part of their routine care) for their anatomical suitability for EVAR with CT (see section 4.1 for further details on patient identification and screening assessment). All patients will undergo post-operative CT between 4 weeks and 3-months post implantation in line with routine local surveillance policies following EVAR and further follow-up to 1-year will be at the discretion of the implanting center.

Patients may be enrolled into the study provided all inclusion and no exclusion criteria are met as specified in Section 4. Procedural details may vary between sites, but all will follow standard hospital

Protocol version 3.1, dated: 11/11/2021

Favourable opinion given by South East Scotland Research Ethics Committee 01 on 12/01/2021

protocol for EVAR and patient care management. Subjects will be evaluated through hospital discharge and return for follow-up visits between 4 weeks and 3 months and at 12 months  $\pm$  4 weeks.

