### **Secondary Endpoints**

- Technical success defined as successful access and deployment of all required EXCC Device components
- In hospital mortality
- Adjuncts to deal with type 1 endoleak at surgery
- Freedom from Type 1 or 3 endoleak at end of procedure, 3 months and 1 year
- One-year aneurysm-related re-intervention rates
- One-year aneurysm-related mortality

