## 6. ASSESSMENT AND FOLLOW-UP

### 6.1 SCHEDULE OF EVENTS

	Screening/ Baseline	Prior to procedure	Procedure	Discharge	1 st follow-up (4 weeks to 3 months post-op)	2 nd follow-up (12 months ± 4 weeks post- op)
Informed Consent (option to recruit before or within 30 days of procedure)	X	X		X	X (within 30 days only)	
Demographics and Medical History	X #	X #				
Physical Examination	X #	X #		X		
Blood results	X #	X #				
ASA risk classification & operative details			X			
SAE assessment (related and unexpected events only)				X	X	X
CT Scan+	X				X	X *
Duplex Ultrasound+						X *

\* 12 months follow-up imaging type (CT or duplex) will be at the discretion of the implanting site.

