## 6.3 PROCEDURE

The Sponsor and the funder will not impose requirements that limit health care professionals from exercising their best medical judgment for treatment. Therefore, patient selection, diagnostic imaging and treatment interventions will be determined by physicians based on clinical practice standards. No specifications for device use, indication, follow-up schedule or requisite data collection outside of the site's routine practice will be required.

Patients who meet the BSET-CLEVAR registry inclusion Criteria and are treated with the Gore Conformable AAA Endoprosthesis with ACTIVE CONTROL System at participating sites will be considered enrolled in the BSET-CLEVAR registry once they sign the study-specific informed consent form, either *before* or *within 30 days* of device implantation.

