## **6.5 FOLLOW-UP**

Follow-up will be as prescribed by the participating institution and/or health care professionals. If a Participant does *not* return to the site for follow-up evaluation, it is requested that the site contact either the patient, patient's next of kin/representative or the patient's GP for survival determination.

A post-operative CT scan must be performed between 4 weeks and 3 months following primary procedure and the images transferred to the Core-Lab, as detailed in section 7.3.

Re-interventions and additional device deployment should be recorded on the Re-interventions CRF.

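### The 12-month follow-up is both scheduled and left to the centre, and the contact with non-attenders asks only about survival, so re-interventions done elsewhere are not actively sought

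*Protocol*

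**What the plan says.** **Statements that schedule the 12-month visit**
- Section 3.1 says subjects "return for follow-up visits between 4 weeks and 3 months and at 12 months", with a window of four weeks either side.
- The Study Summary footnote gives the same window for this visit: "second (final) follow-up, including either a CT scan or duplex U/S imaging (depending on local EVAR surveillance policy), may be done at 12 months".
- The schedule in 6.1 has a column for this visit, with the note that "12 months follow-up imaging type (CT or duplex) will be at the discretion of the implanting site".
- Section 6.7 makes study completion depend on all visits and imaging being done and recorded.

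**Statements that leave follow-up to the centre**
- Section 3.1, just before the scheduled visit is stated: "further follow-up to 1-year will be at the discretion of the implanting center".
- Section 6.3: "No specifications for device use, indication, follow-up schedule or requisite data collection outside of the site's routine practice will be required".
- Section 6.5: "Follow-up will be as prescribed by the participating institution and/or health care professionals".

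**What is collected**
- Section 3.2 lists "One-year aneurysm-related re-intervention rates" and one-year aneurysm-related mortality as secondary endpoints.
- For a participant who does not return, 6.5 asks the site to contact the patient, next of kin or representative, or "GP for survival determination". No other item is named.
- Section 5.2.3 requires every death, with its cause, on the SAE form.
- Sections 6.4 and 6.5 ask that re-interventions be recorded on their own CRF, without tying this to attendance.
- Section 7.2 makes sites responsible for the information needed to confirm endpoints.

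**The concern.** A one-year re-intervention rate needs the re-intervention status of each participant at one year, or at least the date up to which it is known. A site that follows the discretionary wording could omit the 12-month visit and still consider itself within protocol. For those who then do not come back, the one contact that the protocol sets out yields only whether they are alive.

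An event treated at the implanting hospital will normally be known there and can be recorded. An event treated at another hospital in a patient who has stopped attending will not be known unless someone asks. The resulting error runs mainly one way: unknown events are missed, while nothing comparable adds false ones. A later analysis plan can set the denominator or the handling of unknown status, but it cannot recover events that nobody was asked to look for.

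**Working it through.** **Step 1. The protocol's own figure.** Section 8.2 expects 180 to 190 of up to 200 patients to complete, with one-year survival of 90% to 95%.
- 200 × 0.90 = 180
- 200 × 0.95 = 190

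The figure reproduces exactly. Deaths are therefore the only loss counted, and nothing is allowed for survivors who miss the 12-month visit.

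**Step 2. Scheduled or discretionary.** The Study Summary and 6.1 confine the centre's choice to the type of imaging. The sentence in 3.1 speaks of further follow-up in general. Section 6.3 disclaims any follow-up schedule outside routine practice, and 6.5 leaves follow-up to the institution. The narrow and the broad statements cannot both govern what a site must do at 12 months.

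**Step 3. Each endpoint in a non-attender.**

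| Endpoint | What identifies the event | What requires its recording | Gap |
|---|---|---|---|
| Aneurysm-related death | Survival contact in 6.5 | 5.2.3: every death, with cause | 6.5 does not point to 5.2.3 |
| Re-intervention known to the site | Site's own records | 6.4, 6.5, 7.2 | None |
| Re-intervention unknown to the site | No stated step | 6.4 and 7.2, but only once known | Not actively sought |

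**Step 4. Illustration of size.** All inputs here are assumptions, since the protocol gives none of them. Let d be the share of survivors who miss the visit, r the rate in attenders, k the ratio of the non-attenders' rate to r, and f the share of non-attenders' events that the site learns of anyway.
- True rate = (1 − d)·r + d·k·r
- Reported rate, all participants in the denominator = (1 − d)·r + f·d·k·r
- Shortfall = (1 − f)·d·k·r

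Number of non-attenders among 180 to 190 survivors: 9 to 10 at d = 5%, 18 to 19 at d = 10%, and 36 to 38 at d = 20%.

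Results with r = 5%:

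| d | k | f | True | Reported |
|---|---|---|---|---|
| 10% | 1 | 0 | 4.5% + 0.5% = 5.0% | 4.5% |
| 20% | 1 | 0 | 4.0% + 1.0% = 5.0% | 4.0% |
| 10% | 3 | 0 | 4.5% + 1.5% = 6.0% | 4.5% |
| 20% | 3 | 0 | 4.0% + 3.0% = 7.0% | 4.0% |
| 20% | 3 | 0.5 | 7.0% | 4.0% + 1.5% = 5.5% |

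With r = 10%, k = 2 and f = 0, the true rate is 11.0% against 9.0% reported at d = 10%, and 12.0% against 8.0% at d = 20%.

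If only attenders were analysed, the reported rate would be r itself. It would then be too low only if k exceeds 1.

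**The case against.** A reader might infer that, followed as written, the protocol obtains neither one-year re-intervention nor aneurysm-related mortality in those who do not return. The documents do not support that.
- **Deaths.** The survival contact reveals a death, and 5.2.3 then requires its cause, with no exception for missed visits. The general limit of SAE reporting to related and unexpected events does not undo this, because deaths are singled out as always reportable.
- **Re-interventions.** Recording is not tied to attendance (6.4, and again at the end of 6.5). Sites carry a general duty on endpoints (7.2), the co-ordinator pursues missing items (7.3), and three contact attempts precede a declaration of loss (6.6). Events known to the implanting site are covered.

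The contradiction can also be softened. The discretion sentence in 3.1 follows directly on the post-operative CT and may have been meant for imaging only, as 6.1 says. That reading is reasonable for 3.1 alone, but 6.3 and 6.5 are broader and do not fit it.

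Finally, the size rests on assumed inputs. The 7% figure needs both the highest non-attendance and a threefold rate, and the endpoint is secondary and descriptive. All of this stands.

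What remains is that the duties in 6.4 and 7.2 say what to record, not how a site is to learn of an event elsewhere. The one contact described does not ask.

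**Conclusion.** The point holds in a limited form. The passages on 12-month follow-up contradict one another and must be reconciled. Re-interventions unknown to the implanting site have no stated active ascertainment in participants who do not return, so the one-year aneurysm-related re-intervention rate is likely to be understated.

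The size cannot be determined from the protocol. Under the assumptions shown with a 5% rate in attenders, the shortfall runs from 0.5 percentage points (10% non-attendance, equal rates, no event known) to 3.0 points (20%, threefold rate, no event known). It shrinks in proportion as sites learn of events by other routes. Where non-attendance is rare, or nearly all re-interventions take place at the implanting hospital, the effect is negligible.

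It does not follow that aneurysm-related mortality goes uncollected. There the only defect is a missing cross-reference from 6.5 to 5.2.3. The primary endpoint, measured on the first post-operative CT, is not affected. This is a cheap improvement to a secondary endpoint.

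**What to change.** 1. Reconcile the statements on follow-up to one year in the Study Summary, 3.1, 6.1, 6.3, 6.5 and 6.7, so that a site can tell what is expected at 12 months and what is left to local practice. Which of these applies is for the investigators to settle.
2. In 6.5, widen the purpose of the existing non-attender contact. Suggested wording: *For each participant who does not return, the site will establish, from hospital records, the GP, the participant or the next of kin, vital status, any aneurysm-related re-intervention at any hospital with its date, and the date of last contact. Date and cause of any death are reported as in 5.2.3.*

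The re-interventions CRF already exists, so the added items are few. The cost is a slightly longer contact and a record check for each non-attender, plus an amendment, for which 7.6 requires ethics approval. The change to 6.5 concerns data collection only and adds no visit, scan or clinical rule. It cannot recover events that the people contacted do not know of, but the date of last contact then shows how far each participant's status is known.

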## **3.2 STUDY OUTCOME MEASURES**

### **Primary Endpoint**

Evaluation of positioning accuracy and aortic neck coverage expressed as percentage of the total aortic neck assessed by a follow-up CT scan between 4 weeks and 3 months.

Endograft neck utilization will be assessed by Core lab analysis. The surface area of infra-renal neck will be calculated by assessment of the preoperative CT scan. Post-operative CT will be performed between 4 weeks and 3-months and the surface area of aortic neck covered by the GORE® EXCLUDER® Conformable AAA Endoprosthesis with ACTIVE CONTROL System will be calculated as a percentage of the pre-operative surface area.

### **Secondary Endpoints**

- Technical success defined as successful access and deployment of all required EXCC Device components
- In hospital mortality
- Adjuncts to deal with type 1 endoleak at surgery
- Freedom from Type 1 or 3 endoleak at end of procedure, 3 months and 1 year
- One-year aneurysm-related re-intervention rates
- One-year aneurysm-related mortality

## **4. PARTICIPANT ENTRY**

### **4.1 IDENTIFICATION AND SCREENING**

The target patient population for the GORE® EXCLUDER® Conformable AAA Endoprosthesis with ACTIVE CONTROL System registry is a consecutive series of patients who undergo endovascular

treatment for abdominal aortic aneurysm. Prior to study-specific screening, all patients will have had a CT scan as part of their routine care and they will have been identified for routine treatment of their AAA by EVAR after meeting accepted surgical threshold criteria. These patients will then be screened for potential inclusion in the BSET-CLEVAR registry by review of their medical notes by vascular clinicians from the patient's existing clinical care team at the participating hospital or during the vascular multidisciplinary team (MDT) meeting, or in person during a routine appointment at the Vascular Out-patients clinic. If deemed suitable, the patient will be provided with study-specific patient information sheet (PIS) by their Vascular Surgeon or Vascular Specialist Nurse, either in person during a routine appointment (in which case they will be given a minimum of 24 hours to consider participating in the registry), or by post prior to their routine appointment/hospital visit. If the latter, the PIS will be sent to the potential Participant in pre-paid envelopes (provided by the study co-ordinating centre) before the patient's routine vascular out-patients appointment or hospital admission, so that the patient will have had time to read the information before they visit the hospital. They will have opportunity to discuss the information contained in the PIS with their Vascular Surgeon/Vascular Specialist nurse and asked to consider participating in the registry.

Written consent will be obtained from those patients who agree to participate either before *or* after their operation and they will be assigned a study ID number. If written consent is being obtained after EVAR, this will be done within 30 days of implantation. Only patients who meet all of the inclusion criteria and none of the exclusion criteria specified below will be enrolled. At each participating hospital, a log of all screened patients will be kept locally, which will record basic demographic data (patient initials/year of birth/sex; to ensure patients have not been recorded in duplicate) and reasons for non-eligibility.

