## 4.2 INCLUSION CRITERIA

Indication for aortic endovascular stent graft repair as determined by the treating physician.

The patient is / has:

- Age 55 or more at the time of informed consent signature.
- Non-ruptured infra-renal AAA that requires treatment, and in the opinion of the Investigator, whose anatomy is adequate to receive or has already received the GORE® EXCLUDER® Conformable AAA Endoprosthesis **with ACTIVE CONTROL System** (EXCC device).

Protocol version 3.1, dated: 11/11/2021

Favourable opinion given by South East Scotland Research Ethics Committee 01 on 12/01/2021

- An Informed Consent Form dated and signed by the Subject either before *or* within 30 days of EXCC device implantation

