## **7.7 ACCESS TO SOURCE DATA/DOCUMENTS**

Source data are defined as all information necessary for the reconstruction and evaluation of the Clinical Investigation. The local PIs will keep all study records, source data and investigational devices available for inspection by the Sponsor, Study coordinating Centre personnel, Ethics committee and regulatory authorities (also see section 7.1 for auditing & monitoring).

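### Section 4.1 describes a consecutive series, but consent may follow the outcome and no count of all attempted EXCC cases is required, so early rates can look too favourable

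*Protocol*

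**What the plan says.** Protocol 4.1 states that the registry's target population "is a consecutive series of patients who undergo endovascular" treatment of an abdominal aortic aneurysm. Four other provisions decide who actually enters.

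- **Eligibility (4.2).** The patient must be one "whose anatomy is adequate to receive or has already received the" EXCC device, in the investigator's opinion, and must personally have signed the consent form.
- **Selection (6.3).** "patient selection, diagnostic imaging and treatment interventions will be determined by physicians based on clinical practice standards".
- **Enrolment (6.3).** Treated patients who meet the criteria "will be considered enrolled in the BSET-CLEVAR registry once they sign the study-specific informed consent form". Section 4.1 adds: "If written consent is being obtained after EVAR, this will be done within 30 days of implantation". Section 9.2 bars collection of study data before consent.
- **Log (4.1).** At each hospital "a log of all screened patients will be kept locally". It holds basic demographics and "reasons for non-eligibility".

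On oversight, 7.7 says: "The local PIs will keep all study records, source data and investigational devices available for inspection by the Sponsor" and by the co-ordinating centre, among others. Section 7.1 plans visits to all sites to support data collection, image transfer and form completion. Neither section mentions comparing the log with the number of EXCC cases treated.

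**The concern.** In a single-arm registry, the reported rates can be read as the device's rates only if the enrolled patients can be related to everyone treated. The word consecutive tells the reader that this link exists. The protocol sets no rule that creates it.

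The post-operative consent route makes this more than loose wording. Technical success, adjuncts for type 1 endoleak and endoleak at the end of the procedure are all known on the day of surgery. In-hospital mortality will often be settled before day 30. Someone who dies while consent is still to be sought leaves both the numerator and the denominator. Someone with a complicated course may be too unwell to sign, may decline, or may not be approached. Each route removes bad outcomes preferentially, so the error runs in one direction.

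The registry is meant to describe real-world outcomes (Study Summary and section 2) and to supply data for planning a comparative study (section 8). Both uses suffer if the early event rates are too low by an unknown amount. An analysis plan cannot repair this later, because it cannot recover a denominator that was never collected.

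**Working it through.** **Step 1. The protocol's own figure.** Section 8.2 gives up to 200 patients, 1-year survival of 90–95% and 180–190 completers. 200 × 0.90 = 180 and 200 × 0.95 = 190, so the figure reproduces. It starts from enrolled patients and says nothing about who was not enrolled.

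**Step 2. Timing.** The procedural endpoints are fixed on day 0, and in-hospital mortality at discharge or death. Consent is allowed to day 30. For anyone consented after surgery, enrolment is therefore conditional on survival to signature and can depend on the course so far. The 30-day clock also runs from implantation. A case in which access or deployment fails may have no implantation date, and that is the case technical success is meant to count.

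**Step 3. Effect on mortality.** Inputs:

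- m = 0.01, the operative mortality in 8.2, used here as a stand-in for in-hospital mortality.
- f = share of patients due to be consented after surgery. Not in the document; assumed.
- g = share of deaths in that group that precede consent. Not in the document; assumed.

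Observed mortality = m(1 − fg) / (1 − mfg). Expected deaths = 200 × observed mortality. P(no deaths) = (1 − observed mortality)^200.

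| f | g | Observed mortality | Expected deaths in 200 | P(no deaths) |
|---|---|---|---|---|
| 0 | any | 1.00% | 2.0 | 0.13 |
| 0.25 | 1 | 0.75% | 1.50 | 0.22 |
| 0.50 | 0.5 | 0.75% | 1.50 | 0.22 |
| 0.50 | 1 | 0.50% | 1.01 | 0.37 |
| 0.75 | 1 | 0.25% | 0.50 | 0.60 |
| 1 | 0.5 | 0.50% | 1.01 | 0.37 |
| 1 | 1 | 0 | 0 | 1.00 |

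For f = 0.5 and g = 1: 0.01 × 0.5 / (1 − 0.005) = 0.005 / 0.995 = 0.00503, and 200 × 0.00503 = 1.01.

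**Step 4. Effect on technical success.** Let the true success rate be p, and let failures be enrolled with relative probability r compared with successes. Both are assumptions. Observed success = p / (p + (1 − p)r). With p = 0.95 and r = 0.5 this is 0.95 / 0.975 = 97.4%. With p = 0.98 and r = 0.5 it is 0.98 / 0.99 = 99.0%. With r = 1 there is no distortion.

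**Step 5. Could the log show the loss?** It covers screened patients and must give demographics and reasons for non-eligibility. The protocol does not list refusal, not being approached, death before consent or a missed consent window as items to record. It does not ask for the log to be sent to the co-ordinating centre or matched to EXCC cases.

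**The case against.** Several points on the other side are sound, and they limit what can be concluded.

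- **Checkability.** A reader might infer that consecutiveness can never be checked because the log stays at the hospital. The documents do not support that. Section 7.7 opens site records to the sponsor and co-ordinating centre, and 7.1 plans visits to every site. What stands is that no check is specified and the required log content would not be enough for one.
- **Device choice.** A reader might infer that choosing this device breaks the series. Entry by device is inherent in a single-device registry, and the sentence in 4.1 is most naturally read as consecutive recipients of that device. This limits generalisation to all endovascular repair; it is not itself a break.
- **The log may hold more than it appears to.** A signed form is an inclusion criterion (4.2), and unwillingness to comply is an exclusion (4.3). Some refusals and some deaths before consent could therefore be logged as non-eligibility. The protocol does not say so, and patients never screened would still be absent.
- **Size.** One could assume an enrolled fraction and a higher event rate in the rest. For example, 70% enrolled and a threefold rate gives 0.7 + 0.3 × 3 = 1.6 times the reported rate. Neither input is in the document, so the multiplier only restates the assumptions.
- **Primary endpoint.** A reader might extend the point to neck coverage. An event-rate multiplier has no meaning for a median percentage. Patients who die before the CT window opens at 4 weeks are excluded from that analysis whatever their consent status. The window does overlap the last days for consent, but nothing shows a material effect.
- **Sampling error.** A shift from 2 deaths to 1 in 200 is within chance variation for so rare an event. That is true, but chance variation has no direction and this loss does.

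**Conclusion.** The point holds as a gap in enrolment rules and accounting. Section 4.1 states a property that no other provision secures, and consent after the outcome lets deaths and poor early courses drop out. The affected endpoints are in-hospital mortality, technical success, adjunct use and end-of-procedure endoleak, and the bias is towards favourable results.

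The size is unknown, because the protocol does not say how many patients will be consented after surgery or how many deaths will precede consent. On its 1% operative mortality, expected deaths in 200 range from 2.0 (no post-operative consent) through about 1.0 (half consented afterwards, all deaths in that half before consent) to 0 (all consented afterwards, all deaths before consent). The document does not show that selection will occur to any given degree, only that it can occur without being seen. The point should be addressed, but it does not invalidate the registry.

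**What to change.** 1. In 4.1, define the series as all consecutive eligible patients in whom EXCC treatment is attempted at the site, from site opening to closure. Use attempted rather than implanted: a series defined by implantation would leave out failed access or deployment and so select on technical success.
2. Have each site send the co-ordinating centre anonymised aggregate counts by status: consented before surgery, consented after, declined, not approached, died or missed the window before consent, ineligible. Reconcile the total with the site's record of EXCC cases.
3. Report the enrolled fraction overall and by site.
4. Report in-hospital mortality and the procedural endpoints separately for patients consented before and after surgery. The first group is free of this particular selection, though not of refusal or non-approach.
5. If this is not done, delete the word consecutive from 4.1.

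Sections 4.2 and 9.2 should also be reconciled. The first requires the patient's own signature, while the second still allows a legally authorised representative. This bears on whether patients left incapacitated by the procedure can enter.

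This is a cheap improvement: a sentence in 4.1 and a short return of counts, with no added visits, imaging or patient-level data from people who did not consent. The cost is small site effort and lower precision in the two consent-timing groups than in the whole cohort. The sponsor should confirm that aggregate counts are compatible with the bar in 9.2 on collecting study data before consent.
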